50 individuals with trichotillomania or skin picking disorder will be recruited for a double-blind, placebo-controlled pilot study in which dronabinol or placebo is administered in a 1:1 fashion. All 50 subjects will have trichotillomania or skin picking disorder per DSM-5 criteria. Following baseline measures, all subjects will be randomized to either dronabinol or placebo and seen every 2 weeks for the first four weeks and every 3 weeks for the remainder of the 10-week period.

Participants will be started at 5mg po qday for 2 weeks, then 5mg po bid for 2 weeks and then 5mg TID for the remaining 6 weeks. Participants will only go up to the full dose if clinically needed. Efficacy and safety measures will be performed at each visit.

The study will be conducted in accordance with the International Conference on Harmonization Guideline for Good Clinical Practice, all local ethical and legal requirements, and the World Medical Assembly (Declaration of Helsinki). The study protocol and procedures will be approved by the University of Chicago's institutional review board prior to any recruitment. Written informed consent will be required for study participation.

Randomization of drug will be conducted in blocks of eight. The blind will be assessable to the study subject at all times by calling the pharmacy number listed on the medication bottle. The investigational pharmacy will follow proper accountability procedures in regards to both randomization of the study drug and holding of the blind.

Subjects:

Inclusion criteria:

- 1) men and women age 18-65;
- 2) current DSM-5 trichotillomania or skin picking disorder; and
- 3) Ability to understand and sign the consent form.

Exclusion criteria:

- 1) Unstable medical illness based on history or clinically significant abnormalities on baseline physical examination
- 2) Current pregnancy or lactation, or inadequate contraception in women of childbearing potential
- 3) Subjects considered an immediate suicide risk based on the Columbia Suicide Severity rating Scale (C-SSRS) (www.cssrs.columbia.edu/docs)
- 4) Past 12-month DSM-5 diagnosis of psychosis, major depressive disorder, bipolar disorder, mania, or a substance or alcohol use disorder
- 5) Illegal substance use based on urine toxicology screening
- 6) Stable dose of medications for at least the past 3 months
- 7) Previous treatment with dronabinol

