- 8) Cognitive impairment that interferes with the capacity to understand and self-administer medication or provide written informed consent

Baseline Assessments:

Those subjects who appear appropriate for the study, based on telephone screening, will be invited for a baseline assessment. The duration of the baseline assessment will be approximately 90 minutes and will include the following: informed consent, demographic data, concomitant medications (no psychotropic medications will be allowed), and family history data. There will also be a physical examination (including weight, and vital signs, urine pregnancy test for women of childbearing years and urine drug screen, as well as a baseline blood draw to assess nutritional status. The blood draw is optional to the subject and will administered at the PI's discretion). Finally, the subjects will undergo a psychiatric evaluation (using the MINI International Neuropsychiatric Interview).

In addition, the following instruments will be completed at the screening visit: 1) NIMH Trichotillomania Symptom Severity Scale (or the same scale modified for skin picking); 2) Sheehan Disability Scale; 3) Massachusetts General Hospital Hairpulling Scale; 4) the 17-item

Hamilton Rating Scale for Depression (HAM-D); 5) the 17-item Hamilton Rating Scale for Anxiety (HAM-A); 6) Clinical Global Impression (Improvement and Severity) scale; 7) Cambridge Caffeine Use Questionnaire; 8) The Dietary Fat and Free Sugar Questionnaire and 9) the Quality of Life Inventory; 10) Cambridge-Chicago Trait Scale (12); the Skin Picking Symptom Assessment Scale (SP-SAS); and the Body Focused Repetitive Behavior Broad Assessment Measure (BFRB-BAM), a new scale being added for validation purposes. In addition, subjects will undergo cognitive assessments at baseline and study endpoint.

Cognitive Assessments: Assessments of cognitive control will be comprised of several valid paradigms (See below). These tasks are designed to probe dissociable neural circuitry and cognitive processes likely to be implicated in the pathophysiology of addictions. Task order was chosen arbitrarily and will be applied consistently across subjects, to minimize possible confounding factors of differences in task order across participants.

The following tasks will be administered at baseline and final visits:

- Stop Signal Task of Inhibitory Control (SST)
- Intra-dimensional/Extra-dimensional Set Shift Task (ID/ED task)
- One Touch Stockings Task (OTS)

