- Rapid Visual Processing Task (RVP)
- Spatial Working Memory Task (SWM)
- Cambridge Gambling Task (CGT)

Following-Up Visit Assessments

All follow-up visits will include all psychiatric measures (except the MINI which will be done at baseline only) and safety measures (adverse events, vital signs, C-SSRS). There will be four follow up visits for a total of five visits.

Subject Compensation

Subjects will be compensated \$20 per visit, for a total of \$100. Compensation will be given in the form of a check at the end of the study, as per University of Chicago protocol.

Safety Assessments

Safety and tolerability will be assessed using spontaneously reported adverse events data, Columbia–Suicide Severity Rating Scale (C-SSRS), vital signs, and by evaluating premature termination. Safety assessments (C-SSRS, sitting blood pressure, heart rate, adverse effects, and concomitant medications) will be documented at each visit. Subjects who are an immediate suicide risk will be removed from the study and appropriate clinical intervention (e.g. hospitalization) will be arranged. Urine pregnancy tests will be performed at the initial visit. Subjects who have a positive urine pregnancy test will be excluded from the study. Assessment of side effects will be done at each visit. AEs will be coded by system organ class (SOC) and preferred term (PT) using the Medical Dictionary for Regulatory Activities (Med- DRA) Version 11.1. The incidences of all AEs will be summarized descriptively. In terms of vital signs, those subjects with abnormal blood pressures will be assessed for symptoms of hypo- or hypertension. Asymptomatic subjects will be evaluated each visit for changes in vital signs. In the case of hypertensive emergencies (BP greater than 210/120), appropriate referral to the emergency room will be made. In the case of hypotension (BP less than 90/60), participants will be evaluated for symptoms of hypotension and if symptomatic, appropriate interventions will be made.

Seizure and seizure-like activity have been reported in patients receiving dronabinol. Therefore, history of seizures will be an exclusion criterion. If a seizure occurs, dronabinol will be discontinued. Participants will be advised to discontinue dronabinol and contact a healthcare provider immediately if they experience a seizure.

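### Two eligibility wording errors: the seizure-history exclusion is missing from the numbered exclusion list, and exclusion item 6 on stable medication is reversed

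*Combined protocol and SAP*

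**What the plan says.** **Seizures.** The Safety Assessments section notes that seizures have been reported with dronabinol and concludes: "Therefore, history of seizures will be an exclusion criterion". It goes on to argue that new seizures are uncommon once patients with a seizure disorder are left out. The same section states one other entry exclusion: "Subjects who have a positive urine pregnancy test will be excluded from the study".

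**The numbered list.** Under Subjects, the protocol gives three inclusion and eight exclusion criteria. Exclusion item 1 is "Unstable medical illness based on history or clinically significant abnormalities on baseline physical examination". Item 2 is "Current pregnancy or lactation, or inadequate contraception in women of childbearing potential". Item 6 is "Stable dose of medications for at least the past 3 months".

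**Screening.** Baseline Assessments says "Those subjects who appear appropriate for the study, based on telephone screening, will be invited for a baseline assessment", without giving the content of that telephone screen. The baseline visit covers "informed consent, demographic data, concomitant medications (no psychotropic medications will be allowed), and family history data", followed by a physical examination, laboratory tests and a psychiatric interview.

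**The concern.** Eligibility criteria are operative rules: site staff apply them candidate by candidate. Two of them do not work as they stand.

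The seizure rule is a safety exclusion that the investigators thought important enough to state, and their own risk argument leans on it. It is missing from the place where eligibility would normally be checked. At stake is the enrolment of someone with a past seizure whom the protocol means to keep off the drug.

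Item 6 has the opposite sense to any plausible purpose. Followed exactly, it refuses a candidate who has taken a permitted drug at the same dose for months and accepts one whose dose changed last week. The opening section forbids deviating from the protocol without prior IRB approval, except to remove an immediate hazard. Staff who silently read item 6 backwards therefore depart from the approved text, and staff who follow it select the wrong candidates.

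**Working it through.** No arithmetic applies beyond counting. The check sets the sections side by side.

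**Step 1: is the seizure rule in the list?** The eight exclusions cover:

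1. unstable medical illness
2. pregnancy, lactation or inadequate contraception
3. immediate suicide risk
4. listed psychiatric and substance use diagnoses in the past 12 months
5. illegal substance use on urine screening
6. stable dose of medication
7. earlier dronabinol treatment
8. cognitive impairment

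Seizures are named in 0 of 8. Of the two entry exclusions in Safety Assessments, the pregnancy rule is matched by item 2 and the seizure rule by nothing.

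**Step 2: does another item cover it?** Item 1 is the nearest. It requires the illness to be unstable, or an abnormality on physical examination. A single seizure years ago, or a controlled condition, need meet neither test. The pandemic provision under Design/Randomization also allows the baseline visit to be held by video, so less can be left to the examination.

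**Step 3: would a baseline procedure reveal it?** The listed baseline contents name family history and concomitant medications but no seizure question. Item 1 refers to history, so some medical history must be taken, but its content is not specified. Nor is that of the telephone screen.

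**Step 4: does other text correct item 6?** The inclusion criteria concern age, diagnosis and consent, ending with "Ability to understand and sign the consent form". Medication is mentioned in 0 of 3. The only other medication rule at entry is the parenthetical ban on psychotropics in Baseline Assessments, which says nothing about dose stability. Item 6 therefore stands uncorrected:

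| Candidate on a permitted (non-psychotropic) drug | Item 6 read literally | Item 6 with its likely intent |
|---|---|---|
| Dose stable for at least 3 months | excluded | eligible |
| Dose changed within 3 months | eligible | excluded |

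The right-hand column is an inference. Item 6 is most plausibly a lost negation or an inclusion criterion put under the wrong heading.

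**Step 5: do the design figures depend on this?** The Sample Size section uses an effect size, a power and a significance level, none of which involves these criteria. Randomization follows the baseline measures, so an eligibility error acts before allocation and does not favour either arm.

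**The case against.** The strongest reply is that the seizure rule is in the protocol. On the document as a whole, every candidate with a seizure history is excluded, so adding the item changes nobody's eligibility. A miss needs a screener who uses the list and not the safety section. The list is also plainly not the only source of entry rules: the psychotropic ban sits in Baseline Assessments, and the Data Management Plan says the exclusion criteria cover people who need more than outpatient care, which no numbered item states. No eligibility checklist is included, so how screening was done, and how likely a miss would be, is unknown. As for item 6, the literal reading makes so little clinical sense that staff would probably read it as intended.

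Most of this stands, and it limits the point. A reader might infer that the protocol lets patients with past seizures in. It does not, because Safety Assessments excludes them. A reader might also infer that literal item 6 is a useful accidental bar to patients on a stable seizure drug, so that correcting it alone would open a door. That holds only if Safety Assessments is ignored, item 6 is applied word for word, the seizure drug is not counted as psychotropic, and item 1 is not met. The documents do not support treating this as a real interaction. Nor do they show that anyone was screened under the literal item 6.

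The reply does not remove the inconsistency itself. The list and the safety section give different sets of exclusions on a safety matter, and having entry rules scattered elsewhere makes an incomplete list harder to use. An eligibility rule should not depend on readers reversing it.

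**Conclusion.** Both errors are real and confined to wording. The exclusion list is inconsistent with Safety Assessments because it omits history of seizures, and item 6 says the reverse of what it evidently should. Together, one stated safety exclusion is missing from a list of eight, and one of the eight runs the wrong way.

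The conclusion about the seizure rule rests on the text alone. The harm from it is conditional on screening being done mainly from the list, which the documents neither show nor rule out. The literal meaning of item 6 is also plain from the text; its intended meaning is inferred and needs the sponsor's confirmation. The number of candidates affected by either error cannot be estimated from the documents. The trial's statistical conclusions are not threatened. The reasons to correct the text are participant safety and a clear definition of who may enter.

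**What to change.** Make two edits in one amendment.

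- **Seizures.** Add *History of seizures* to the numbered exclusions, and ask about it at telephone screening or baseline. Keep this wording, which is that of the stated rule. The later phrase in the same section, seizure disorder, is narrower and would leave out an isolated seizure.
- **Item 6.** After the sponsor confirms the intent, reword it to exclude candidates whose medication dose has not been stable for at least the past 3 months. List the psychotropic ban from Baseline Assessments beside it, so that both medication rules stand together. The documents give no basis for writing in further rules, such as allowances for as-needed or short-course drugs; the sponsor should decide whether any are wanted.

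The cost is one short IRB amendment and one or two screening questions, with no added test or visit. The seizure edit excludes no one whom the protocol does not already exclude. The net effect of correcting item 6 on recruitment cannot be estimated from the documents.

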Given the serious personal consequences associated with trichotillomania and skin picking disorder, and the likelihood of success of dronabinol in treating both disorders, the aim of the present study was to examine the efficacy and safety of dronabinol vs placebo in adults with trichotillomania or skin picking disorder using a double-blind, placebo-controlled design.

We hypothesize that dronabinol will be more effective than placebo in reducing the frequency of hair pulling and skin picking and in improving overall psychosocial functioning after 10 weeks of treatment when compared to baseline.

Primary Aim/Objective

The aim of the present study is to examine the efficacy and safety of dronabinol vs placebo in adults with trichotillomania and skin picking disorder.

Co-Primary Endpoint(s):

The co-primary efficacy measures will be the change in hair pulling or skin picking frequency and urges to pull hair or pick skin for the past week as indicated by change in total score on the *NIMH Trichotillomania Symptom Severity Scale* (for TTM) or *Skin Picking Symptom Assessment Scale* (for SPD), reliable and valid clinician-administered measures (18-19), as well as the same scale modified for skin picking disorder, and the change in psychosocial functioning over the same time period using the *Sheehan Disability Scale* (20). The co-primary efficacy end points will be the change in these measures from baseline to week 10.

Secondary Aim/Objective

A secondary aim of the study is to examine the effects of dronabinol vs placebo on self-report measures of hair pulling, skin picking, quality of life, and measures of mood and anxiety.

Secondary Endpoint(s):

Secondary efficacy measures include the change in number of days per week pulling, the *Clinical Global Impressions–Improvement Scale* (CGI-I) rated global improvement of symptoms over time (results will be dichotomized as improved [CGI-I ratings of 1 or 2 very much/much improved] or not improved [CGI-I ratings of 3-7]) (20), the self-report *Massachusetts General Hospital Hairpulling Scale* (22), the *Skin Picking Symptom Assessment Scale*, the *Quality of Life Inventory* (23), the *Hamilton Depression Rating Scale* (24), the *Hamilton Anxiety Rating Scale* (25), and the *Tridimensional Personality Questionnaire*

Methodology

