- Any moderate adverse event which appears definitely, probably, or possibly related to study participation will be reported to the University of Chicago IRB in writing within 20 working days.
- Any mild adverse event will be summarized in the IRB annual progress reports.

Statistical Analysis

Design/Randomization

The study is a double-blind, placebo-controlled study. Participants will be randomized (1:1) to receive dronabinol or placebo by the University of Chicago Investigational pharmacy in block sizes of eight, using computer-generated randomization with no clinical information.

Due to the pandemic of COVID19, study participants can perform their baseline and follow-up visits online using encrypted Zoom instead of in person visits. All inventories will be assessed. Blood samples and urine toxicology, however, will be at the discretion of the study PI. In cases where they are considered medically necessary, the participant can have them drawn locally and submitted to the study team.

Efficacy Analysis

For statistical analysis, the full-analysis set will be defined as all participants who took at least 1 dose of the study drug and had at least 1 post-randomization primary efficacy assessment. The safety-analysis set will be defined as all randomized participants who took at least 1 dose of the study drug and completed at least 1 post-randomization safety assessment. Participants with trichotillomania and skin picking disorder will be grouped as one BFRB group.

We will compare the baseline characteristics of both groups using Fisher's exact test for categorical variables and the t test for continuous variables. We will calculate adherence to treatment, based on the number of pills returned at each visit, as the number of pills taken divided by the number of days in the study $\times 100\%$.

Primary endpoint analysis

The primary outcome measure will be the change from first randomization visit to study endpoint in total composite score on the NIMH Trichotillomania Symptom Severity Scale(s) and the Sheehan Disability Scale.

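### The symptom co-primary pools two diagnoses rated on different scales or versions, but diagnosis enters neither the randomisation nor the primary model

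*Combined protocol and SAP*

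**What the plan says.** **Sample and allocation.** Under Methodology, "50 individuals with trichotillomania or skin picking disorder will be recruited for a double-blind, placebo-controlled pilot study". Allocation is 1:1 in blocks of eight, stated there and again under Design/Randomization ("in block sizes of eight, using computer-generated randomization with no clinical information"). Neither section names a stratification factor.

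**Pooling.** Under Efficacy Analysis: "Participants with trichotillomania and skin picking disorder will be grouped as one BFRB group".

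**Symptom scale.** The sections disagree on skin picking.
- Co-Primary Endpoint(s) gives the NIMH scale to trichotillomania and the Skin Picking Symptom Assessment Scale (SP-SAS) to skin picking, then adds "as well as the same scale modified for skin picking disorder".
- Baseline Assessments lists the "NIMH Trichotillomania Symptom Severity Scale (or the same scale modified for skin picking"), and lists the SP-SAS separately.
- Primary endpoint analysis names only the NIMH scale, with an optional plural. Secondary endpoints analyses treats the SP-SAS as a self-report secondary measure.

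**Other co-primary.** The Sheehan Disability Scale is used for both disorders.

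**Primary model.** ANOVA on change, last observation carried forward, with treatment as the only term named. No diagnosis term, standardised score or within-diagnosis analysis appears.

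**Dual diagnosis.** The inclusion criterion is met by either disorder and does not exclude having both. No rule names the index disorder.

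**The concern.** Diagnosis decides which instrument, or which version, produces the symptom score. The documents do not say that a point on one equals a point on the other. If mean change differs between the two, each arm's mean depends partly on its mix of diagnoses.

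At about 25 per arm the mix will vary by chance. Randomisation does not restrain it and the model does not remove it. Two things are at stake: power in an already small trial, and how the one estimate is read if the split turns out uneven. A participant with both disorders could also have two candidate primary scores, with nothing to say which one counts.

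**Working it through.** **Inputs from the documents.** Total 50, 1:1, blocks of eight; effect size 0.5; alpha .05; 80% power; treatment-only ANOVA on change.

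**Assumptions, because the documents give no figure.** Trichotillomania share p = 0.5, 0.7 or 0.8. D, the difference between diagnoses in mean change, = 0.25, 0.5, 1.0 or 1.5 within-diagnosis SD. Tests two-sided (sidedness is not stated).

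**Step 1: the plan's own figure.** n per group = 2(z_alpha + z_power)² / 0.5².
- One-sided: 8 × (1.645 + 0.842)² = 49.5, so 50. This is the stated number per group.
- Two-sided: 8 × (1.960 + 0.842)² = 62.8, so 63.

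The 0.5 is used below as the benchmark. With 25 per arm, two-sided power at 0.5 is 0.41 before any case-mix noise. The gap between 50 per group and 50 in total is a separate matter.

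**Step 2: how uneven the arms become.** The SD of the between-arm difference in share is approximately √[p(1−p)(1/25 + 1/25)].
- p = 0.5: √(0.25 × 0.08) = 0.141
- p = 0.7: √(0.21 × 0.08) = 0.130
- p = 0.8: √(0.16 × 0.08) = 0.113

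Simulating blocks of eight gives the same SDs. The difference reaches 20 points in about 18 to 19%, 15% and 10% of trials respectively. At 50:50 the median absolute difference is about 8 points and the 95th percentile is 28. If the counts are fixed exactly instead, with 25 per arm, the 20-point probability is 26% for 25 trichotillomania participants, 15% for 30, 22% for 35 and 7% for 40. These values are uneven because the counts are discrete.

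**Step 3: shift from a 20-point imbalance** (for example 15 of 25 against 10 of 25). Shift = 0.20 × D.

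**Step 4: average power at a true effect of 0.5, p = 0.5.** Without a diagnosis term the residual SD is √[1 + p(1−p)D²], so the effective effect is 0.5 divided by that. At D = 1 this is 0.5/√1.25 = 0.447.

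| D (assumed) | Shift, SD | Share of 0.5 | Effective effect | Power, no term | Power, diagnosis term |
|---|---|---|---|---|---|
| 0.25 | 0.05 | 10% | 0.496 | 0.40 | about 0.40 |
| 0.5 | 0.10 | 20% | 0.485 | 0.39 | about 0.40 |
| 1.0 | 0.20 | 40% | 0.447 | 0.34 | about 0.40 |
| 1.5 | 0.30 | 60% | 0.400 | 0.28 | about 0.40 |

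Over all randomisations, type I error is about 0.05 with either analysis.

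**Step 5: one unlucky trial.** With a 15 v 10 split and D = 1, unadjusted power is 59% if the imbalance favours drug and 13% if it goes against drug. With no true effect the test rejects in 6.8% of such trials, nearly all in one direction.

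**Step 6: stratification alone.** Stratified blocks of 4 cut the SD of the imbalance to about 3 points. If the model still omits diagnosis, power at D = 1 is 0.32, no better than the 0.34 above, because the between-diagnosis variance stays in the error term.

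**The case against.** The strongest reply is that chance imbalance is not bias. Its variation is already in the t-test standard error, and type I error holds. That stands. A reader might infer that the planned test is invalid or favours drug; the documents do not support that.

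Second, D may be small. The Background says the two disorders may share a neurobiology and respond to the same interventions. At D = 0.25 the shift is 0.05 SD and the diagnosis term gains nothing on average. This stands as a reason to show a range and not a single figure. It does not show that D is near zero, because similar clinical response need not mean similar point changes on different instruments. If skin picking is scored on a modified NIMH scale with the same range, D may well be smaller.

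Third, the Sheehan co-primary is one scale for both disorders. That stands: it is affected only if the diagnoses change differently on it.

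Four further inferences go beyond the text:
- That diagnosis was deliberately kept out. The phrase about clinical information may simply describe allocation concealment, and a single list is itself inferred from the absence of strata.
- That a large imbalance is likely. Roughly 80 to 90% of trials stay below 20 points.
- That the scale for a dual-diagnosis participant will be picked afterwards. The documents are only silent on it.
- That comparable arms within each disorder are required. The plan makes one pooled comparison.

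**Conclusion.** The point holds for the symptom co-primary, as a matter of precision and interpretability and not of validity. Diagnosis determines the scale or version, is known at baseline, and appears in neither the allocation nor the primary model. The average cost is power: nothing measurable at D = 0.25, about 0.06 at D = 1 (0.40 to 0.34) and about 0.12 at D = 1.5 (0.40 to 0.28). In an unlucky trial the estimate can move by 10 to 60% of the planned effect. All of these sizes rest on the assumed D and case mix. The missing model term matters more than the missing stratification. The unresolved choice of skin picking scale and the missing index-diagnosis rule are gaps whatever D is. The change is worth making before unblinding because it is nearly free.

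**What to change.** 1. Reconcile Co-Primary Endpoint(s), Baseline Assessments and the Statistical Analysis section so that one named symptom scale serves as primary for skin picking.
2. Record each participant's index diagnosis, and hence the one primary symptom scale, before assignment. If enrolment is complete, fix it from baseline records before unblinding. Cost: one field on the randomisation request.
3. Add index diagnosis as a term in the primary ANOVA. Cost: one residual degree of freedom.
4. Consider standardising symptom change within scale, for example dividing by that scale's baseline SD pooled over arms. A diagnosis term removes an additive shift but does not make points on two instruments comparable. Cost: the effect is no longer in scale points.
5. Optionally, for participants not yet randomised, have the pharmacy stratify by index diagnosis with blocks shorter than eight, and only together with item 3. Cost: a second list, and assignments that are somewhat easier to guess.
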